2.2. Secondary objectives

1. To assess the non-invasive strategy as compared to the invasive usual strategy for the management of patients regarding vasopressor-free days at day 28, organ failure progression, fluid balance, and duration of mechanical ventilation support.
2. To assess the impact of the non-invasive strategy on the number of lab tests ordered, the number of vascular punctures performed, the magnitude of related pain reported by the patients, the evolution of blood haemoglobin level, the number of red cell transfusions administered during the ICU stay, the number of catheter-related infections, and on the direct hospital medical costs of care.
3. To determine the efficiency of the non-invasive strategy when compared to the recommended invasive strategy (ICER: 'Cost/Life day gained at 28 days').
4. To evaluate the budget impact of the generalization of the non-invasive strategy (in case of demonstrated non inferiority) in France from the viewpoint of the French health system on a 5 years' time frame

2.3. **Outcome measures**

Primary outcome measure

All-cause mortality by 28 days after randomisation

Secondary outcome measures

- To account for the potential bias brought by deaths occurring as the result of life-sustaining treatments withdrawal/withholding, as frequently encountered in ICUS, we will record such events from inclusion to Day 35 (i.e., until one week after the primary time point)(56)
- Cumulative incidence of death from inclusion through Day 90
- Cumulative survival free of IAC insertion, from inclusion through Day 90
- Number of patients who underwent IAC insertion, in both groups
- Evolution of daily Sequential Organ Failure Assessment (SOFA)(57) score during the first seven days
- Daily amount of intravenous fluid given for rapid vascular volume expansion from Day 1 to Day 7
- Daily fluid balance from Day 1 to Day 7
- Duration of mechanical ventilation
- Ventilator-free days from Day 1 to Day 28 (for this purpose patients dying between randomisation and Day 28 will be assigned a 0 value; for survivors at Day 28, all the days free of invasive mechanical ventilation through an endotracheal tube within the 28-day period will be taken into account)
- Proportion of patients treated by renal-replacement therapy between Day 1 and Day 28

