6.1. Sample size

In a non-inferiority randomised clinical trial, we usually hypothesize *a priori* an equal incidence of the event of interest in the two groups compared. In the present study, our *a priori* hypothesis is different. Indeed, we expect a marginal benefit of the non-invasive approach, because the systematic IAC insertion may harm the patients through catheter-related infections and through blood spoliation. However, even demonstrating that the non-invasive approach is not inferior to the systematic IAC insertion approach could be considered as a positive result (cf., Risk/benefit ratio section).

We therefore assume that the mortality rate at day 28 will be 22.5% in experimental group and 25% in the control group. We set the non-inferiority margin at 5%, power at 80% and alpha risk at 5%. Such hypotheses led us to plan the inclusion of 1010 patients.

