In the usual care group, the proportion of patients who underwent IAC is a measure of adherence. In the experimental group, the proportion of patients who underwent IAC is of relevance as it reflects the limits of the non-invasive approach.

- The effect of intervention on changes over time of the SOFA score, the blood haemoglobin level, haematocrit, mean daily blood volume drawn for lab testing, mean daily amount of intravenous fluids given for rapid vascular volume expansion, mean daily fluid balance, daily maximum pain and associated 95%CI will be estimated using mixed linear models, after data transformation if necessary.
- Duration of mechanical ventilation will be analysed using a competing risk approach, with death as competing risk.
- The effect of intervention on proportion of patients treated by renal-replacement therapy or by vasopressor, proportions of patients with arterial and central venous catheter-related infections or bloodstream infections and associated 95%CI will be estimated using the competing risk approach, with death as competing risk.
- The effect of intervention on number of blood cultures performed, number of attempts at arterial puncture, number of red blood cell packs transfused, number of arterial and central venous catheter insertion and associated 95%CI will be estimated using negative binomial models with duration of ICU stays as offset variable.
- Two-sided 95% CIs of median differences of free-days (Ventilator-free days, renal replacement therapy-free days, vasopressor therapy-free days) will be estimated.
- Duration of ICU and hospital stay: 2-sided 95% CIs of median differences will be estimated.

- The effect of intervention on ICU and hospital mortality and 95% CI will be estimated using competing-risk model with ICU and hospital discharge alive as competing events with death during the stay.

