The primary analysis of the primary outcome will be the determination of the between-group difference (noninvasive group minus invasive group) in rates of day-28 mortality, estimated with a binomial generalized estimating equation (GEE) model with identity link adjusted on the stratification variables and on the center effect (Pedroza 10.1186/s12874-016-0217-0). A switch from noninferiority to superiority is *a priori* planned if the hypothesis of noninferiority with a noninferiority margin of 5 percentage points is verified. These hypotheses will be assessed using the stratified Farrington-Manning test for differences in proportions.

Secondary outcomes analysis

Statistical analyses for secondary outcomes will not be adjusted for multiplicity; therefore, secondary-outcome findings should be interpreted as exploratory.

- Day-90 mortality will be analyzed with the same model as the primary outcome .
- Cumulative incidence of death from randomization through Day 90 will be analyzed with a Cox model.
- ICU mortality and hospital mortality will be analyzed in a competing risks framework. A hazard ratio will be computed from the whole groups using a Fine and Gray regression model. ICU discharge or hospital discharge will be considered as competing events.

The following outcomes will be described with median and quartiles and compared between groups using median differences:

- Duration of ICU stay from randomization to discharge.
- Duration of hospital stay from randomization to discharge.
- Duration of mechanical ventilation from randomization and Day 28.
- Ventilator-free days from randomization to Day 28.
- Renal replacement therapy-free days from randomization to Day 28.
- Vasopressor therapy-free days from randomization to Day 28.

For each outcome, 95% confidence intervals of the median difference will be computed using unstratified bootstrapping (10,000 samples with replacement). Vasopressor therapy-free days, renal replacement therapy-free days and duration of mechanical ventilation do not account for the competing risk of death.

The following outcomes will be represented with boxplots at each day:

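### Read literally, the ventilator-free-days rule scores days ventilated through a tracheostomy as ventilator-free; a minor scoring error in an exploratory outcome, corrected by one phrase

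*Protocol*

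**What the plan says.** The definition stands in Protocol section 2.3 (Outcome measures, secondary). For deaths, "patients dying between randomisation and Day 28 will be assigned a 0 value". For Day-28 survivors, "all the days free of invasive mechanical ventilation through an endotracheal tube within the 28-day period will be taken into account". Section 6.2 plans the comparison as "Two-sided 95% CIs of median differences of free-days".

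The SAP (Secondary outcomes analysis) lists "Ventilator-free days from randomization to Day 28" with no definition of its own. It reports medians and quartiles and compares arms by the median difference with a bootstrap interval. The same list holds "Duration of mechanical ventilation from randomization and Day 28", which carries no airway restriction in either document. The SAP says that, without multiplicity adjustment, "secondary-outcome findings should be interpreted as exploratory".

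Tracheostomy is not mentioned in either document. It is not a non-inclusion criterion (Protocol 4.3). Stratification uses invasive mechanical ventilation, yes or no, without reference to the type of tube (Protocol 4.1).

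**The concern.** A patient who is tracheostomised and stays on the ventilator no longer has an endotracheal tube. Under the rule as worded, each later ventilated day is free of ventilation through such a tube and is credited. A patient already ventilated through a tracheostomy at enrolment could be stratified as ventilated and still score 28.

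Two things are at stake. First, the two ventilation outcomes can disagree about the same day. Second, the SAP states that duration of mechanical ventilation does not account for the competing risk of death. Ventilator-free days, with deaths scored 0, is therefore the ventilation outcome that takes death into account, and its scoring should be right.

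**Working it through.** **1. The plan's own figure.** The only design figure that can be reproduced is the sample size. Protocol 6.1 assumes "the mortality rate at day 28 will be 22.5% in experimental group and 25% in the control group", a margin of 5 points and 80% power; section 6.2 uses a two-sided 95% interval, that is one-sided 2.5%. Per arm: (0.25 × 0.75 + 0.225 × 0.775) × (1.960 + 0.842)² / (0.05 + 0.025)² = 0.361875 × 7.849 / 0.005625 ≈ 505, so 1010 in total, as stated. Ventilator-free days do not enter it.

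**2. One patient.** Let V be a survivor's days of invasive ventilation by any tube and E the days through an endotracheal tube. The score counting all invasive ventilation is 28 − V; the literal score is 28 − E; the excess is V − E, the days ventilated through a tracheostomy. Ventilated on all 28 days and tracheostomised after Day 10: 28 − 10 = 18 against 28 − 28 = 0. With the endotracheal tube in place for 7, 14 or 21 days, the literal scores are 21, 14 and 7, each against 0.

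**3. Arm mean.** If a share s of an arm are survivors ventilated through a tracheostomy for d days on average, the mean rises by s × d. From s = 1%, d = 5 to s = 10%, d = 14 (assumed), that is 0.05 to 1.4 days.

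**4. Simulation.** Taken from the Protocol: Day-28 mortality 25% and 22.5%. Assumed: 67% of patients ventilated; lognormal duration, log-SD 1, median 5, 7 or 10 days; the same durations in both arms; tracheostomy after Day 7, 10 or 14 in 25% or 50% of those still ventilated. There were 400,000 patients per scenario and 36 scenarios. Paired median scores are for 25% / 22.5% mortality and are the same at either tracheostomy share.

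| Median duration | Correct median score | Literal, Day 7 | Literal, Day 10 | Literal, Day 14 | Mean overstated by |
|---|---|---|---|---|---|
| 5 days | 22 / 23 | 22 / 23 | 22 / 23 | 22 / 23 | 0.15 to 0.77 |
| 7 days | 20 / 21 | 21 / 21 | 20 / 21 | 20 / 21 | 0.26 to 1.21 |
| 10 days | 17 / 18 | 21 / 21 | 18 / 18 | 17 / 18 | 0.44 to 1.83 |

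The median moves by 0 or 1 day in 32 of the 36 scenarios. It moves by 3 or 4 only with median ventilation of 10 days and tracheostomy after Day 7.

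The pattern has a simple reason. With tracheostomy after Day T, the literal rule changes only scores below 28 − T and raises them to 28 − T. The median therefore cannot move by more than the larger of 0 and (28 − T − correct median). For the last row at 25% mortality this bound is 21 − 17 = 4, 18 − 17 = 1, and 0, which is what the table shows.

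**5. Timing not fixed.** With tracheostomy days spread around 7, 10 or 14 (SD 4 days, assumed), the median moves by 0 or 1 day in 27 of 36 scenarios, by 2 in five, and by 3 or 4 in four, all four with median ventilation of 10 days. The mean is overstated by about 0.2 to 1.9 days.

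**6. Lower quartile.** With mortality near 25%, the lower quartile sits where deaths scored 0 meet the longest-ventilated survivors, so it is sensitive. With median ventilation of 5 days, it rises from 1 to 4 or 9 at 22.5% mortality and stays at 0 at 25%.

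**7. A second set of assumptions.** With 23.75% mortality, 50% or 70% ventilated, median duration 6 days, log-SD 0.9, and tracheostomy on Day 11 or 15 in 25% to 100% of those still ventilated, the median did not move (24 or 21). The lower quartile rose from 0 to between 4 and 18 in some scenarios.

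**The case against.** The strongest reply is that the wording is merely loose. The phrase may be meant to separate invasive from mask ventilation, the CRF coding is not visible, and if the CRF records invasive ventilation as yes or no, tracheostomy days may already be counted as ventilated. This is possible, and it is why the point rests on a literal reading. It does not remove the point: the word invasive already excludes mask ventilation, so naming the tube can only narrow the rule further, and nothing in the SAP widens it again.

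It is also fair that secondary objective 1 (Protocol 2.2) names duration of ventilation support, not ventilator-free days, and that the outcome is exploratory. Both limit the importance.

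Two stronger readings are tempting, and the documents do not support either.

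- A reader might infer that the longest-ventilated survivors in general are scored as liberated. Only survivors who receive a tracheostomy are affected, and only for ventilated days after it. Those who keep an endotracheal tube are scored correctly, and deaths score 0 either way.
- A reader might infer that the rule hides a real treatment effect or creates a false one. In the table, medians of 17 and 18 do merge at 21 or 18. But both arms share one duration distribution, so the 1-day gap comes from the assumed mortality difference and whole-day scoring, not from a ventilation effect. A false difference would need tracheostomy use or timing to differ by arm. The open-label design allows that, but no passage suggests it.

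**Conclusion.** The point stands as a minor scoring error. As worded, the rule credits days ventilated through a tracheostomy as ventilator-free, and it can contradict duration of mechanical ventilation on the same day. The excess for an affected survivor is exactly the number of such days. At arm level its size cannot be computed from the documents. Under the fixed-day assumptions above, the mean is overstated by roughly 0.15 to 1.8 days, the lower quartile can shift, and the compared median usually moves by 0 to 1 day. Larger median shifts need long ventilation together with early or variable tracheostomy timing. No bias between arms is shown. The primary outcome, the margin and the 1010 patients are unaffected.

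**What to change.** In Protocol section 2.3, extend the tube named in the ventilator-free-days definition to *an endotracheal or tracheostomy tube*. Repeat that definition beside ventilator-free days in the SAP, and state that duration of mechanical ventilation uses the same definition of invasive ventilation. Noninvasive ventilation stays excluded from ventilator-free days, as now. If the data were in fact coded on any invasive airway, only the text needs correcting; if not, the affected survivors need rescoring.

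The cost is one phrase in each document plus the alignment sentence. Respiratory status and ventilator settings are already among the listed follow-up assessments (Protocol 4.6), although the documents do not show whether the airway type is recorded. The downside is that reported ventilator-free days become slightly less favourable in both arms.

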3.1. Differences between the usual care and the non-invasive care strategies

Description of blood pressure monitoring among randomisation group

In the “usual care” group, BP will be monitored through the arterial line sensor connected to the usual monitoring device (fluid-filled system). Site of IAC insertion, insertion technique, skin antisepsis and catheter care will be at the discretion of the attending physician, according to local guidelines. Non-invasive BP monitoring is not allowed, except when IAC is considered futile (as defined above) and during IAC insertion or replacement.

In the “non-invasive” group, automated oscillometric monitor will be used to monitor BP. ***The size of the cuff will be adapted according of the arm circumference and manufacturer recommendations.*** The dedicated indicator will be placed at the level of the artery. If deemed appropriate according to clinical context, the cuff may be placed at the lower limb.(30)

In both groups, alarm thresholds and interval of BP measurements will be left at the discretion of the attending physician.

Blood sampling technique

In the “usual care” group, blood samples for lab tests will be drawn from the IAC, as many times as

necessary. Blood-drawing through the central venous catheter is forbidden, excepted for ScvO₂ measurements.

In the “non-invasive” group, blood-drawing through the central venous catheter is recommended for usual lab tests. To avoid interruption or bolus on specific continuous therapeutics, we strongly recommend infusing vasopressor agents in a dedicated line of the central venous catheter that should not be the line used for sampling. Regarding the monitoring of ventilation parameters and of the lactate blood level, we encourage the attending intensivists and investigators to rely on SpO₂ (60,61) to assess oxygenation, and on predicted pH, PaCO₂, and lactate derived from central venous blood analysis.(47) For this purpose, formula to derive estimates of arterial blood parameters and abacuses giving probabilities of true arterial values below or above given thresholds for each predicted value will be provided to the sites (APPENDIX 2).

Arterial blood gas parameters

We will develop a mobile application to automatically estimate arterial blood gas parameters from central venous parameters and SpO₂ (see APPENDIX 2). As the study is not cluster randomized, the mobile app with the arterial blood parameters calculator will be available for all investigators regardless whether they are in charge of patients randomized in the “invasive” (presence of IAC) or the non-invasive group. To minimize this potential source of bias, we want to emphasise, and this will be clearly reminded in the mobile app, that central venous blood drawing will not be allowed in the “invasive” group, except for ScvO₂ measurements.

Modalities of patients' general management

In both group, patients will be managed following international and national guidelines, except for the IAC insertion.

Regarding blood sampling for lab tests, to avoid unnecessary blood spoliation in both arms, we strongly encourage investigators and attending intensivists to properly assess the real need of each lab test ordered. We discourage sampling for routine (daily or more frequent) monitoring or after changes in FiO₂ or PEEP. If blood gas were drawn for suspicion of metabolic or respiratory disorder, only the control after therapeutic intervention will be allowed.

In addition, to decrease blood spoliation during sampling through any vascular catheter (IAC for the invasive group, CVC for the non invasive group), we strongly suggest to apply the following procedure that may help minimizing the discard volume of blood withdrawn before the sampling.(62,63)

After cleaning the catheter hub, draw off 3 mL (for sampling through IAC) or 5 mL (through CVC) of blood (i.e., at least 2 times the catheter's priming volume)(64) with a syringe and waste the syringe. Draw the blood sample through the Vacutainer system. Be sure to sample blood from a line of the catheter not dedicated to continuous vasopressor therapy (to avoid bolus or discontinuous infusion).

4. Study design

The projected study will be a multi-centre, pragmatic, randomised, controlled, open, two-parallel-group, non-inferiority clinical trial with 1:1 assignment of interventions.

Although blinding is not possible due to the nature of the assessed intervention, the primary endpoint is objective (mortality at day 28). The trial will associate medical, surgical, and mixed ICUs, as well as academic tertiary care hospitals and community hospitals.

We deliberately decided not to perform a cluster-randomized trial. This design is prone to the risk of selection bias. Moreover, there are few centres in the study, which could lead to chance imbalance.

As the need for IAC insertion is rooted in intensivists' mind when caring for patients in shock, there is a real risk that patients assigned to the non-invasive arm will frequently be switched to the invasive arm (with IAC insertion). To prevent this kind of contamination bias, the study scientific committee has set reasonable and consensual safety boundaries that will fix in which circumstances the insertion of an IAC will become an inescapable need (in terms of vasopressor requirement for instance [see the "3. *Interventions*" paragraph]). In the end, we opted for a classical standard individually randomised trial and worked at limiting group contamination.

4.1. Randomisation

Randomisation will be electronically centralised via a dedicated website.

Randomisation will be stratified on centres, invasive mechanical ventilation (yes or no) and vasopressor dosage, namely < or \geq 0.18 μ g/kg/mn of continuous iv norepinephrine (ie. 0.36 μ g/kg/mn of continuous iv norepinephrine tartrate) or of epinephrine or of the sum of both medications dosages at time of enrolment.

The statistician in charge of the project will determine permutation blocks, the size of which will not be known by the investigators.

4.2. Study time points definitions

Patients will be declared enrolled in the study once consent obtained.

Date and time of randomisation will determine the beginning of the intervention period (Study H0)

4.3. Inclusion and non-inclusion criteria

Inclusion criteria

- Age \geq 18 years the day of inclusion
- Existence of an acute circulatory failure defined by the presence of the following items 1 and 2:
 - 1) Persisting hypotension (systolic blood pressure less than 90 mmHg or mean arterial blood pressure less than 65 mmHg) for more than 15 min at ICU admission or within the following

24 hours, **OR** requirement of continuous iv vasopressor treatment (i.e. any dose of norepinephrine / epinephrine)

- 2) Presence at least one of the following signs of hypoperfusion: alteration of mental status; skin mottling; oliguria defined as a urine output < 0.5 mL/kg body weight for at least one hour; arterial lactate > 2 mmol/L; peripheral venous lactate > 3.2 mmol/L; ScvO₂ <70%
- Free express oral and informed consent of the patient or a proxy in case of impossibility for the patient to consent; emergency inclusion possible when legal representatives and patient's family are not available
- French health insurance holder

Non-inclusion criteria

- Acute circulatory failure, as defined by items 1 and 2 in inclusion criteria list (cf. supra) present for more than 24 hours
- NIBP device fails to display a BP value, or cuff placement impossible
- Patient for whom an ECMO therapy (either veno-arterial or venous-venous) is already in place or is to be initiated within the next 6 hours
- Patient treated with vasopressor doses of more than 2.5 µg/kg/min of *norepinephrine tartrate* plus epinephrine for at least 2 hours (i.e., for instance, more than 8 mg of *norepinephrine tartrate* in 50 mL at the rate of 66 mL/hour for a patient weighing 70 kg) (*please note that in fact this dosage corresponds to 1.25 µg/kg/min of norepinephrine base*)
- Severe traumatic brain injury (i.e., traumatic brain injury with a Glasgow coma scale score of less than 9 before sedation)
- Patient previously included in the trial
- Body mass index (BMI) above 40 kg/m² (33,35,65)
- Pregnancy
- Brain death
- Moribund patient
- Patient known, at time of inclusion, as being under guardianship, tutorship or curatorship

[figure not shown]
N.B.: Note that a patient already carrying an indwelling arterial catheter can still be randomized in the study provided that all the above criteria are respected. If randomised in the “noninvasive group”, the catheter should be removed within one hour following randomisation.

